4.2 Inclusion and exclusion criteria

Selection criteria and verification methods are described in the table below.

Inclusion criteria	Verification methods
Drug injection within the last 30 days	Self-declaration AND confirmation by healthcare worker (presence of punctures on the participant’s body from injection drug use)
14 years old and older as of the survey period	Self-declaration AND visual control by coupon-manager
Not less than 1 month of residence/work/surveying in the area where	Self-declaration

⁸ Lisa G. Johnston (Tulane University), Keith M. Sabin (UNAIDS), “Sampling hard-to-reach populations with respondent driven sampling”, Methodological Innovations Online (2010), 5(2) 38-48

survey is conducted	
Informed consent to participate in all survey components, namely: (1) questionnaire completion; (2) capillary blood collection with EDTA K3 blood micro containers (microtainers) for further rapid testing for HIV, hepatitis C and syphilis; second HIV diagnostic rapid testing in case of positive results; dry blood spot (DBS) for further testing to detect recent HIV infection and viral load level	Signed informed consent to participate in the survey

Exclusion criteria	Verification methods
Repeated participation in one survey round	Self-declaration OR visual identification of a repeated attempt by coupon-manager
Refusal to participate in one or several survey components	Absence of signed informed consent to participate in the survey
Alcohol or drugs intoxication, which does not allow to understand and answer questions of the questionnaire, and the respondent's behavior threatens his own safety or the safety of others	Visual control by coupon-manager

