10.1 Multiplier method

The multiplier method is based on availability of at least two overlapping data sources specific to the population of interest, one being a count or registry of unique individuals belonging to the population, and another one being a representative survey that assessed whether the participants are present in the first data source. The data sources have to be independent of each other; define the target group in the same way; present the same time period, age and target group geography; be of sufficient data quality.

The formula to calculate the population size using the multiplier method is: $N = M/P$, Where:

N = Estimated Size

P = Proportion of survey participants who reported belonging to the registry (receiving the service, the object, or participating in the survey).

M = Number of individuals in the registry.

The 95% confidence intervals for proportions calculated for descriptive statistics using bootstrapping method with RDS weights will be used to calculate the lower- and upper limits for the population estimates.

The following data sources and indicators will be used for the multiplier method:

#	PSE indicator	Questionnaire item	Existing registry	Data provider
1	Registration in drug treatment clinics	Are you registered with the state narcological clinic in connection with drugs abuse or addiction?	Currently undetermined. Previously: Reporting form No.11 "Report on the morbidity of individuals with mental and behavioral disorders due to psychoactive substance use", annual. Table 2120 "Number of individuals with mental disorders due to intravenous drug use". Indicator: "among people under the supervision at the end of the reporting period".	Regional and city state drug treatment clinics.

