2	Substance use treatment	Were you getting treatment in the state narcological clinic in 2022? (in-patient treatment / out-patient treatment) Have you been getting treatment in the state narcological clinic in 2023 (January-March)? (in-patient treatment / out-patient treatment)	Currently undetermined. Previously: Reporting form No.11 "Report on morbidity of individuals with mental and behavioral disorders due to psychoactive substance use", annual. Table 2300 "Composition of individuals in a drug treatment in-patient clinic". Indicator: "Mental and behavioral disorders due to the use of opioids, cannabinoids, cocaine, hallucinogens, combinations of several drugs and other psychoactive substances, total" Currently undetermined. Previously: Form No.11 "Report on the morbidity of individuals with mental and behavioral disorders due to psychoactive substance use", annual. Table 2100 "Contingent and treatment of individuals with mental disorders due to psychoactive substance use". Indicator: "Mental and behavioral disorders due to opioid use – covered with in-patient/out-patient treatment". Includes data on the number of people registered with a substance abuse clinic, who have already completed in-patient treatment at the end of the reporting period, including those, who have been treated at day drug treatment in-patient clinics.	Regional and city state drug treatment clinics.
3	Criminal	Have you been detained by the police in 2022?	Number of people notified of suspicion under articles	Statistical data

	prosecution	Have you been detained by the police in 2023?	307 and/or 309 during 2019 and 2023. Identified people who committed criminal offences under articles 307 and/or 309 during 2022 and 2023. Committed criminal offences under the influence of drugs, toxic and psychotropic substances under articles 307 and/or 309 during 2022 and 2023.	of the city police and the prosecutor's office.
4	Medications for opioid use disorder (MOUD) coverage	Have you received methadone or buprenorphine within the MOUD program in 2022? Are you taking methadone or buprenorphine within the MOUD program (January-March 2023)?	Number of people who were receiving MOUD in all city medical facilities during 2022. Number of people who were receiving MOUD in all city medical facilities during January-March 2023.	Public Health Center

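### The MOUD multiplier (10.1, row 4) divides a count of all MOUD patients by a proportion measured only in current injectors, so it overstates city size by 1/q if only a share q of patients would be survey-eligible and the other assumptions hold

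*Protocol*

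**What the plan says.** Section 10.1 of the protocol estimates city size as N = M/P. M is the number of individuals in a registry, and P is the "Proportion of survey participants who reported belonging to the registry". Among the conditions it sets for the two sources is that they "define the target group in the same way".

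Row 4 of the table applies this to medication for opioid use disorder (MOUD). For one period M is the "Number of people who were receiving MOUD in all city medical facilities during 2022"; for the other it is the "Number of people who were receiving MOUD in all city medical facilities during January-March 2023". The questionnaire items ask about methadone or buprenorphine within the MOUD programme over the same two periods, so question and count agree in service and time. The data provider is the Public Health Center.

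Survey entry is set in section 4.2. The first criterion is "Drug injection within the last 30 days", verified by self-declaration and by a healthcare worker who confirms puncture marks.

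The note below the table provides for trend checks and, where double counting is found, a correction coefficient. Section 10.4.1 drops estimates below NGO prevention coverage or above 4% of the adult population. Section 10.4.2 forms the final estimate from the intersection of ranges, averaging and an anchored multiplier that gives narrower intervals more weight.

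**The concern.** A MOUD patient who no longer injects is counted in M but cannot enter the survey, and so cannot contribute to P. The ratio then sets a wider group over a proportion measured in a narrower one. Row 4 therefore fails the condition that section 10.1 sets. The 2022 item adds to the gap: someone treated in 2022 who stopped injecting before the survey is in M and not in P.

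The row 4 estimates are inputs to the city consensus, which 10.4.2 treats as final and passes to further calculations. City size is used for the population weights in 9.2 and 9.4. A size estimate multiplied by prevalence gives the number of PWID living with HIV in 9.6. The registry data are also collected outside the survey cities so that estimates can be extrapolated.

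**Working it through.** The protocol reports no MOUD multiplier result, so there is no figure to reproduce. The check is algebra on its own formula, followed by an illustration.

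**Inputs**
- Estimator N = M/P, with M all MOUD patients in the city: section 10.1.
- P measured in people who injected in the last 30 days: section 4.2.
- q, the share of MOUD patients who would meet 4.2: not in the protocol; assumed 0.50 to 1.
- Illustration: 33,700 PWID in Kyiv (section 16.0, 2017 figure); about 18,000 MOUD patients nationally (section 2.0); 350,500 PWID nationally in 2017 (section 2.0). That Kyiv has the national ratio of MOUD patients to PWID is an assumption.
- Precision: 500 per city less 5% missing, so n = 475, and design effect 3.0 (section 4.4).

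**Algebra.** Of M patients, qM can be sampled. If the survey recruits them at their population rate, reports are accurate and geography matches, then

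P = qM/N, so M/P = M ÷ (qM/N) = N/q.

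The factor 1/q depends on neither M nor city size. Replacing M by qM gives qM/P = N for any q.

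**Illustration.** 18,000/350,500 = 5.14%, so M = 0.0514 × 33,700 ≈ 1,731.

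| q | P = qM/N | M/P | Ratio to N |
|---|---|---|---|
| 1.00 | 5.14% | 33,700 | 1.00 |
| 0.95 | 4.88% | 35,474 | 1.05 |
| 0.75 | 3.85% | 44,933 | 1.33 |
| 0.50 | 2.57% | 67,400 | 2.00 |

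**Precision of the row 4 estimate.** The half-width for P is 1.96 × √(3P(1−P)/475), a simple asymptotic stand-in for the planned bootstrap. Section 10.1 builds the limits for N from the interval for P.
- q = 1: P from 1.70% to 8.57%, so N from about 20,200 to 102,000.
- q = 0.75: P from 0.85% to 6.85%, so N from about 25,300 to 202,600.

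The intervals are wide, so an anchored multiplier would give row 4 little weight. They still reflect sampling error in P only; nothing in them represents uncertainty about q.

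**Safeguards compared with the mechanism**
- Correction coefficient (note to 10.1): for double counting. A patient who has stopped injecting is counted once.
- Plausible range (10.4.1): removes a value only if it crosses a limit. An inflated value inside the range stays.
- Intersection and interval-width weighting (10.4.2): responds to overlap and precision, not to whether M and P describe the same group.

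**City weights.** The weight for city c is N_c/ΣN. If every N_c is multiplied by the same factor k, then kN_c/ΣkN = N_c/ΣN, and the weights do not change.

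**The case against.** The strongest reply is that the size of the error is unknown and may be small. No section gives q, and a value of 0.95, which means a 5% error, fits the protocol as well as 0.50 does. This stands. A reader might infer from the purpose of MOUD that q must be far below 1 and the estimate grossly inflated; nothing in the protocol supports a particular value.

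Second, the upward direction is conditional. Seeds are chosen partly by whether they are prevention-programme clients (6.3), and one month of residence or work in the area is enough for entry (4.2). If treated injectors were over-recruited, P would rise and M/P would fall. This also stands. A reader might infer that row 4 is too high in every city, or can serve as an upper bound; neither follows, because another bias could act downward.

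Third, row 4 is one of eleven indicators, its interval is wide, and non-overlapping or extreme estimates lose influence or are excluded. That dilutes the error but does not remove it, and the protocol does not allow the part that reaches the consensus to be calculated.

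Fourth, a factor common to all city sizes cancels in the weights. This is correct, so the weights are affected only so far as q, and with it the inflation, differs between cities. The cancellation does not extend to absolute numbers of PWID.

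Fifth, row 4 is not the only row affected. Row 2 includes a registry of in-patients covering cannabinoids and hallucinogens, and row 3 counts people under two criminal articles; neither is limited to people who inject. This widens the point rather than answering it. Rows 5 to 11 word their counts as PWID or concern PWID services, so row 4 is less well matched than those.

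**Conclusion.** The point holds in a conditional form. Row 4 as written does not meet the condition in 10.1 that both sources describe the same group, and no step in 10.1 or 10.4 takes non-injecting patients out of M. If the other multiplier assumptions hold and some MOUD patients no longer meet 4.2, the row 4 estimate exceeds N by the factor 1/q: 1.05 at q = 0.95, 1.33 at 0.75 and 2 at 0.50. The values of q are assumptions. The effect on the city consensus is smaller than these factors, by an amount that cannot be derived from the protocol.

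One further reading goes too far. Section 4.2 might be taken to require puncture marks made in the last 30 days. It requires self-declared injection in that period and the presence of punctures; the marks are not dated. The mismatch with M does not depend on dating them.

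This should be corrected before the size estimation, but it does not undermine the other indicators in the table or the survey itself.

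**What to change.** In 10.1, state that M in row 4 is multiplied by a documented share of MOUD patients who still inject, with the source named and the uncertainty of that share carried into the limits for N. The Public Health Center is already the data provider for this row, but the protocol does not say whether its programme data record current injecting, so this must be established first.

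In 10.4.2, state that where no such share is available, row 4 is kept out of both the intersection of ranges and the anchored-multiplier consensus and is reported as a sensitivity estimate, not as an upper bound.

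Apply the same check against the 10.1 condition to rows 2 and 3 before their estimates enter the consensus.

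The cost is a sentence or two in each section. The downside is one fewer indicator in the consensus wherever the share is unknown, at a time when the registries for rows 1 and 2 are themselves still undetermined.

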5	Harm reduction coverage	Are you a client of any NGO working with people who inject drugs (have a client's card or an individual code)? Have you received free sterile needles/syringes from a non-governmental organization within the last 12 months (March 2022-March 2023)? Have you received free condoms from a non-governmental organization within the last 12 months (March 2022-March 2023)? Have you received HIV testing services from a non-governmental organization within the last 12 months (March 2022-March 2023)?	Number of PWID who received any harm reduction services in March 2022-March 2023.	SYREX database
6	Needle and syringe program coverage	Have you received sterile needles/syringes from a non-governmental organization within the last 3 months (January-March 2023)?	Number of PWID who have received syringes/needles within NGO network (average indicator for 3 months).	SYREX database
7	Condom programming coverage	Have you received condoms from a non-governmental organization within the last 3 months (January-March 2023)?	Number of PWID who have received condoms within NGO network (average indicator for 3 months).	SYREX database
8	HIV testing coverage	Were you tested with a rapid test for HIV in non-governmental organization in 2022? Were you tested with a rapid test for HIV in non-governmental organization in 2023 (January-March)?	Number of PWID who have been tested with the HIV rapid tests for 2022 and 2023 (separately for each year).	SYREX database
9	HCV testing	Did you get a rapid test for hepatitis C at NGO	Number of PWID who have been tested with the HCV	SYREX

	coverage	in 2022? Did you get a rapid test for hepatitis C at NGO in 2023 (January-March)?	rapid tests for 2022 and 2023 (separately for each year).	database
10	HBV testing coverage	Did you get a rapid test for hepatitis B at NGO in 2022? Did you get a rapid test for hepatitis B at NGO in 2023 (January-March)?	Number of PWID who have been tested with the HBV rapid tests for 2022 and 2023 (separately for each year).	SYREX database
11	Syphilis testing coverage	Did you get a rapid test for syphilis at NGO in 2022? Did you get a rapid test for syphilis at NGO in 2023 (January-March)?	Number of PWID who have been tested with the syphilis rapid tests for 2022 and 2023 (separately for each year).	SYREX database

These data will be collected for both IBBS and non-IBBS regions, to enable extrapolation of estimates.

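### The needle/syringe and condom multipliers (section 10.1, rows 6 and 7) divide an undefined 3-month average count by a cumulative 3-month proportion; if monthly counts are averaged, both size estimates come out low

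*Protocol*

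**What the plan says.** Protocol section 10.1 uses N = M/P, with "M = Number of individuals in the registry" and "P = Proportion of survey participants who reported belonging to the registry". It sets two conditions that matter here. One source must be "one being a count or registry of unique individuals belonging to the population", and the two sources must "present the same time period, age and target group geography".

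In the table of indicators:

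- **Row 6, question for P:** "Have you received sterile needles/syringes from a non-governmental organization within the last 3 months (January-March 2023".
- **Row 6, registry figure for M:** "Number of PWID who have received syringes/needles within NGO network (average indicator for 3 months".
- **Row 7, question for P:** "Have you received condoms from a non-governmental organization within the last 3 months (January-March 2023".
- **Row 7, registry figure for M:** "Number of PWID who have received condoms within NGO network (average indicator for 3 months".

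Both registry figures come from SYREX. Neither row says what is averaged or names the months. By contrast, row 4 (2023 part) and row 5 ask the registry for the number of people over the whole window, and row 5 uses the same database.

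The limits for N are derived from the bootstrap interval for P. The note under the table foresees a correction only for double counting. Section 10.4.1 excludes estimates outside a range bounded below by NGO prevention coverage and above by 4% of the adult population. Section 10.4.2 combines the remaining estimates.

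**The concern.** N = M/P works only if M counts the same people whom P describes. In rows 6 and 7, P is cumulative: one receipt at any time in the quarter is enough for a yes. An average over the three months is not cumulative. If monthly counts are averaged, a client who came once in the quarter adds one to the numerator of P but only one third to M. The two sources then do not meet the section's own conditions of unique persons and a common period.

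Such an error runs in one direction and does not shrink with sample size. Population size is a stated objective (section 3.0). It enters the planned city weights (sections 9.2 and 9.4) and the count of PWID living with HIV (section 9.6). The registry data are also collected for non-IBBS regions for extrapolation, so the definition matters beyond the surveyed cities.

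**Working it through.** The protocol gives no M, P or N for these rows, so there is no figure of its own to reproduce. The check is algebra plus an assumed range.

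**Inputs**

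- N = M/P and the definitions of M and P: section 10.1.
- P is any receipt in the 3 months: rows 6 and 7.
- M is the mean of the three monthly unique-client counts: an assumption, the natural reading of the undefined average.
- k is the mean number of months, out of three, in which a client of the quarter was served: not in the documents, range 1 to 3.
- Illustrative true N = 33,700: the 2017 figure for Kyiv City in section 16.0.
- n = 500, 5% missing, design effect 3: section 4.4.

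**Step 1. Ratio of estimate to truth.** Let U be the number of different clients served at any time in the quarter. Then P = U/N. The three monthly counts add up to U × k, so M = U × k/3. Hence

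M/P = (U × k/3) / (U/N) = N × k/3.

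Coverage cancels. The ratio k/3 cannot exceed 1, and it equals 1 only if every client is served in all three months. Example with P = 0.45 and k = 2: U = 0.45 × 33,700 = 15,165; M = 15,165 × 2/3 = 10,110; M/P = 22,467.

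| k | k/3 | M/P if true N = 33,700 | Understatement |
|---|---|---|---|
| 1 | 0.33 | 11,233 | 67% |
| 1.5 | 0.50 | 16,850 | 50% |
| 2 | 0.67 | 22,467 | 33% |
| 2.5 | 0.83 | 28,083 | 17% |
| 3 | 1.00 | 33,700 | 0% |

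**Step 2. A model for k.** Assume that each client is served in a given month with probability q, independently between months. Then k/3 = q / (1 − (1 − q)³).

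| q | 1 − (1 − q)³ | Ratio | Understatement |
|---|---|---|---|
| 0.3 | 0.657 | 0.46 | 54% |
| 0.5 | 0.875 | 0.57 | 43% |
| 0.7 | 0.973 | 0.72 | 28% |
| 0.9 | 0.999 | 0.90 | 10% |

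**Step 3. Do the limits for N cover it?** With 475 usable records, the half-width for P is 1.96 × √(3P(1 − P)/475). At P = 0.60 this is 0.076, so the limits run from 0.60/0.676 = 0.89 to 0.60/0.524 = 1.15 times the estimate. At P = 0.30 it is 0.071, giving 0.81 to 1.31.

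- k = 2: the upper limit is 0.67 × 1.15 = 0.77 of the true N at P = 0.60, and 0.67 × 1.31 = 0.88 at P = 0.30. Both miss the true size.
- k = 2.5: the upper limit is 0.83 × 1.15 = 0.95 at P = 0.60 (a miss), and 0.83 × 1.31 = 1.09 at P = 0.30 (covered).

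M is treated as exact, so any coverage at the mild end is by chance.

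**Step 4. Does the floor catch it?** As an illustration only, set the section 10.4.1 floor at 60% of N, the national needle/syringe coverage cited in section 2.0. An estimate is dropped if k/3 < 0.60, that is k < 1.8. The q = 0.3 and 0.5 cases are dropped. The q = 0.7 and 0.9 cases pass uncorrected.

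**Step 5. After the change.** With M = U, M/P = U/(U/N) = N, a ratio of 1.00.

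**The case against.** The strongest objection is that the average is undefined, so the bias is conditional. If quarterly unique counts were averaged, the downward error shown above would not arise. This stands, and the direction should be stated only for the monthly reading. It does not clear the rows: an average of several quarters would still not be the January-March 2023 count that the question calls for.

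Second, these are two of eleven indicator rows, and recapture and successive-sampling estimates are added. The range check may remove the lowest values, and the triangulation favours the region where most ranges overlap. This also stands. The percentages above belong to the two single estimates, not to the consensus. The range check, however, only excludes; it does not correct an estimate that passes.

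Third, double counting would inflate M and push N up, so the net error is open. That is right. But the planned correction for double counting would remove only that offset and leave the averaging error in place.

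A reader might also infer three stronger points that the documents do not support:

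- **That irregular clients are left out of M.** They are counted fractionally, as one third or two thirds.
- **That rows 6 and 7 set the validation range.** Section 10.4.1 sets the floor from NGO prevention coverage and does not name these rows; as written, their estimates are screened against it.
- **That the city weights and the HIV-positive count are off by these percentages.** Weights depend on relative sizes, so a similar proportional error in every city largely cancels. Section 9.6 uses whichever size estimate is most recent, which need not be this round's.

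**Conclusion.** The point holds as a mismatch between M and P in rows 6 and 7. M is an undefined average, P is a cumulative 3-month share, and this conflicts with the conditions stated in the same section.

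On the natural reading, each of the two estimates is understated by 0% to 67% from this source. The size depends on k, which the documents do not give. The 28% and 10% figures rest on assumed monthly service probabilities of 0.7 and 0.9 and on independence between months. The interval for N is not built to reflect this error, and no planned step corrects it.

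It would be tempting to conclude that the final city sizes are biased low by a known amount. The documents do not support that: the averaging unit is undefined, double counting acts the other way, and many other inputs dilute the effect by an amount that cannot be derived. This should be fixed, but it does not by itself invalidate the population size exercise.

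**What to change.** In section 10.1, rows 6 and 7, delete the averaging phrase and define M as the number of different clients, deduplicated by client code in SYREX, with at least one needle or syringe issue (row 6) or condom issue (row 7) in the city during the exact months named in the question. Apply the same definition to the non-IBBS regions, so that any extrapolation rests on like counts.

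The cost is a changed registry query and a table edit, with nothing added for participants. Row 5 already asks SYREX for a whole-period person count, which suggests that this is feasible. The documents do not say whether client codes deduplicate across NGOs, so confirm that with the data provider first. If a quarterly distinct count cannot be produced, asking about receipt in a single month and pairing it with that month's count would also align M and P, at the cost of a questionnaire change.
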